3.2 Exclusion Criteria

The subject must be excluded from participating in the trial if the subject:

3.2.1 Has locally advanced or metastatic disease as determined by CT scan or MRI.

3.2.2 Tumors with histologic features in addition to an adenocarcinoma component are excluded. Variant histologies include but are not limited to adenosquamous, squamous, neuroendocrine, undifferentiated with osteoclast like giant cells, acinar, hepatoid, medullary carcinomas.

3.2.3 Has either had any prior chemotherapy or targeted small molecule therapy, or

immunotherapy or radiation therapy for pancreatic cancer.

Note: If subject received major surgery for reason other than pancreatic cancer they must have recovered adequately from the toxicity and/or complications from the intervention prior to starting therapy.

3.2.4 Has a known prior or current synchronous malignancy, except:

- Malignancy that was treated with curative intent and for which there has been no known active disease for >5 years prior to enrollment
- Curatively treated non-melanoma skin cancer, cervical cancer in situ or prostatic intraepithelial neoplasia, without evidence of prostate cancer.

3.2.5 Significant history of uncontrolled cardiac disease defined as uncontrolled hypertension (defined by a systolic BP ≥ 160 mm Hg and/or diastolic BP ≥ 100 mm Hg), unstable angina, myocardial infarction within the last 4 months, or uncontrolled congestive heart failure. Subjects with a history of cardiac disease should have a clinical risk assessment of cardiac function using the New York Heart Association Functional Classification. To be eligible for this trial, participants should be class 2B or better.

3.2.6 Has a medical history or current diagnosis of myocarditis.

3.2.7 Has a left ventricular ejection fraction $< 50\%$, cardiac valvulopathy $>$ grade 2, or elevated cardiac enzymes (troponin I) elevation $> 2 \times$ ULN.

3.2.8 Has a condition/s that are considered to have a high risk of clinically significant GI bleed or any other condition associated with or history of significant bleeding.

3.2.9 Has a diagnosis of immunodeficiency or is receiving systemic steroid therapy or any other form of immunosuppressive therapy within 7 days prior to the first dose of trial treatment. Patients receiving physiological replacement doses of corticosteroids (10mg of prednisone or equivalent) are allowed.

3.2.10 Has known active, uncontrolled HIV (high viral load), Hepatitis B (e.g., HBsAg reactive) or Hepatitis C (e.g., HCV RNA [qualitative] is detected).

- a. Patients who have been vaccinated for hepatitis B and do not have a history of infection are eligible.

3.2.11 Has received a live vaccine within 30 days prior to the first dose of trial treatment.

COVID-19 vaccination or booster is permitted any time prior to enrollment or during treatment on trial, in a manner consistent with individual institutional guidelines.

3.2.12 Has an active autoimmune disease requiring systemic treatment within the past 3 months or a documented history of clinically severe autoimmune disease, or a syndrome that requires systemic steroids or immunosuppressive agents. Subjects with vitiligo or resolved childhood asthma/atopy would be an exception to this rule. Subjects that require intermittent use of bronchodilators or local steroid injections would not be excluded from the study. Subjects with hypothyroidism stable on hormone replacement or Sjorgen's syndrome will not be excluded from the study.

3.2.13 Has an active serious infection requiring systemic therapy.

3.2.14 Has known psychiatric or substance abuse disorders that would interfere with cooperation with the requirements of the trial.

3.2.15 Subject is unable or unwilling to participate in a study related procedure.

3.2.16 Is pregnant or breastfeeding or expecting to conceive or father children within the projected duration of the trial, starting with the pre-screening or screening visit through 120 days after the last dose of trial treatment.

3.3 Inclusion of Women and Minorities

Both men and women of all races and ethnic groups are eligible for this trial.

4 REGISTRATION And Randomization PROCEDURES

4.1 General Guidelines for DF/HCC Institutions

Institutions will register eligible participants in the Clinical Trials Management System (CTMS) OnCore. Registrations must occur prior to the initiation of any protocol-specific therapy or intervention. Any participant not registered to the protocol before protocol-specific therapy or intervention begins will be considered ineligible and registration will be denied.

An investigator will confirm eligibility criteria and a member of the study team will complete the protocol-specific eligibility checklist.

The eligibility checklist(s) and all pages of the consent form(s) will be emailed to the ODQ at [contact]. The ODQ will (a) review the eligibility checklist, (b) register the participant on the protocol, and (c) randomize the participant.

Randomization can only occur during ODQ business hours (8:30am - 5pm Eastern Time, Monday through Friday excluding holidays).

An email confirmation of the registration and/or randomization will be sent to the study coordinator(s) from the registering site, treating investigator and registering person immediately following the registration and/or randomization.

Following registration, participants may begin protocol-specific therapy and/or intervention. Issues that would cause treatment delays should be discussed with the Principal Investigator (PI) of the registering site. If the subject does not receive protocol therapy following registration, the subject must be taken off study in the CTMS (OnCore) with an appropriate date and reason entered.

4.2 Registration Process for DF/HCC Institutions

Applicable DF/HCC policy (REGIST-101) must be followed.

4.3 GENERAL GUIDELINES FOR OTHER INVESTIGATIVE SITES

Eligible participants will be entered on study centrally at the Dana-Farber Cancer Institute by the Project Manager. All sites should contact the Project Manager to verify dose level availabilities. The required forms can be found in **Section 4.4**.

Following registration, participants should begin protocol therapy within 5 days. Issues that would cause treatment delays should be discussed with the Sponsor-Investigator. If the subject does not receive protocol therapy following registration, the subject must be taken off study in the CTMS (OnCore) with an appropriate date and reason entered.

4.4 Registration Process for Other Investigative Sites

To register a participant, the following documents should be completed by the participating site and e-mailed to the Project Manager:

- Signed participant consent form
- HIPAA authorization form
- Eligibility checklist
- Screening provider note including medical/surgical history, ECOG performance status, vital signs, and physical exam findings
- Pathology report confirming pancreatic cancer (adenocarcinoma, squamous, or adenosquamous histologies)
- Laboratory reports including:
 - CBC with differential
 - Chemistry panel
 - Pregnancy test (if applicable)
 - Cardiac enzymes

- Screening imaging report (CT and/or MRI scans)
- Screening EKG
- Screening echocardiogram

To complete the registration process, the Project Manager will follow DF/HCC policy (REGIST-101) and register the participant on the protocol. The registering party will email the participant study number and assigned arm or dose treatment level to the participating site.

NOTE: Registration can only be conducted during the regular business hours of 8:30 AM to 4:30 PM Eastern Standard Time Monday through Friday, holidays excluded. Same day treatment registrations will only be accepted with prior notice and discussion with the DF/HCC Project Manager.

5 TREATMENT PLAN

5.1. Treatment Regimen

The defined trial treatment to be used in this trial is outlined below in Table 2. Patients will be randomized 2:1 to Arms A and B, the combination of mFOLFIRINOX with NIS793 and mFOLFIRINOX, respectively. Arm A will accrue 30 patients and arm B will accrue a total of 15 patients. Treatment with NIS793 will not be blinded.

Table 2. Trial treatment

Regimen Description					
Arm	Fluorouracil (mg/m ² IV on days 1 over 46 hours of a 14-day cycle)	Leucovorin (mg/m ² IV on days 1 of a 14-day cycle)	Irinotecan (mg/m ² IV on days 1 of a 14-day cycle)	Oxaliplatin (mg/m ² IV on days 1 of a 14-day cycle)	NIS793 (mg/m ² IV on days 1 of a 14-day cycle)
A	2400 mg/m ²	400 mg/m ²	150 mg/m ²	85 mg/m ²	2100mg
B	2400 mg/m ²	400 mg/m ²	150 mg/m ²	85 mg/m ² .	

Appropriate dose modifications are described in Section 6. Reported adverse events and potential risks are described in Section 7. No investigational or commercial agents or therapies other than those described below may be administered with the intent to treat the participant's malignancy.

5.2. Pre-Treatment Criteria

Cycle 1, Day 1, and Subsequent Cycles:

- History and physical exam with vital signs, body weight, and height (obtained within 2 weeks (14 days)).

Laboratories will be collected as follows:

- Hematological profile: CBC with differential on day 1 of each cycle
- Complete metabolic profile: Electrolytes, BUN, creatinine, liver function tests (albumin, total protein, AST, ALT, alkaline phosphatase, total bilirubin), and magnesium on day 1 of each cycle
- Tumor marker profile: CA 19-9 and CEA on day 1 of each cycle
- ANC must be ≥ 1500 for eligibility and Cycle 1 Day 1. Subsequent ANC must be ≥ 1000 .

*For all laboratory measures a window of up to 3 days prior to treatment day is acceptable.

*Baseline laboratory values obtained on Day 1 Cycle 1, with the exception of ANC as noted above, will not affect the patient's eligibility to participate in the study after the patient has undergone successful screening and randomization.

*Results must be available prior to the administration of study drug.

Imaging studies will be performed as follows:

- Chest/Abdomen/Pelvis CT scan or Chest CT scan and Abdomen/Pelvis MRI must be performed within 28 days of the date of registration. In case of CT abdomen/pelvis is used as the radiographic modality it should be protocolled specifically for evaluation of pancreas i.e. Pancreas protocol CT.

5.3 Agent Administration

5.3.1 IND Agent: NIS793

NIS793 will be administered at a fixed dose of 2100mg via IV infusion every 14 days +3/-1 days, before administration of FOLFIRINOX.

NIS793 will be supplied in a vial as liquid concentrate for infusion. At the appropriate time, infuse the volume of the infusion bag with a maximum administration time of 60 minutes. Shorter infusion times can be applied with a minimum infusion time of 30 minutes. The selection of infusion speed within that requirement is the responsibility of the project-responsible clinician and needs to comply with the specs given by the pump. Infusion must take place in a facility with appropriate resuscitation equipment available at the bedside, and a physician readily available during the period of drug administration.

Per sponsor, Baxter: Long primary flush tubing with 0.2 micron filter extension set add-on (PVC-containing) (for volumes \leq 150 ml) 2R8537 + 1C8363 are acceptable to be used. In addition, needles with a length of 2" or longer are recommended as a standard dimension, which was also used in Technical Research and Development (TRD) compatibility studies with NIS793. Shorter needles may be used as long as correct dosing is assured. In terms of needle diameter, gauge numbers equal to or larger than 21G are recommended, so 22 or 23G needles are fine as well.

Participants should be closely observed for potential infusion-related reactions including rigors, chills, wheezing, pruritus, flushing, rash, hypotension, hypoxemia, and fever, and vital signs monitored more frequently if clinically indicated, during and for at least 2 hours after the first two NIS793 infusions. No pre-medications are to be administered during the observation window. The same may apply for the subsequent NIS793 infusions if medically indicated. Participants should notify study personnel if symptoms of infusion reaction occur after any NIS793 infusion. Further instructions for the preparation and dispensation of NIS793 are described in the study pharmacy manual.

Management and dose modifications associated with the administration of NI793 are outlined in Section 6.

Other Agent(s)

5.3.2 mFOLFIRINOX

All participants on both arms will receive mFOLFIRINOX, consisting of 5-Fluorouracil (5-FU), Oxaliplatin, Irinotecan, and Leucovorin. These drugs are commercially available. A central line will be placed for these infusions.

Given that mFOLFIRINOX is standard of care, study treatment will be continued as per institutional standard of care.

No pre-medications for mFOLFIRINOX are to be administered during the NIS793 observation window.

The FOLFIRINOX regimen will be administered intravenously. Treatment will be every 14 days +3/-1 days at physician discretion (unless a further delay is mandated by toxicity criteria). There will be eight cycles of FOLFIRINOX, with each cycle being 14 days in length. Treatment will be administered on an *outpatient* basis. Participants enrolled on Arm A will be treated with mFOLFIRINOX chemotherapy as per institutional standards with NIS793 at 2100mg IV every 2 weeks. Participants enrolled on Arm B will be treated with mFOLFIRINOX chemotherapy alone as per institutional standards.

Dosing schedules and modifications: all commercially supplied drugs will follow the manufacturer-provided labeling with respect to its storage and stability, preparation, handling, and administration. Decisions regarding dose modifications, and delays will be made for each patient at the discretion of the attending physician. All other treatments, including chemotherapy pre-medications, will be determined at the discretion of the attending physician.

All treatments, anti-emetics, and supportive medications should follow institutional guidelines. Subcutaneous growth factor support will be administered between 0 and 72 hours after

discontinuation of continuous infusion of 5-FU in all patients receiving FOLFIRINOX after each cycle. Participants may self-administer at home or have the injection administered in clinic.

5.3.3 Restaging during/after FOLFIRINOX +/- NIS793

Participants will be restaged after four cycles of therapy (interim scans) and following the completion of induction mFOLFIRINOX (after eight cycles of therapy). Restaging scans can be performed after mFOLFIRINOX C4 and C8 pump disconnect (at the earliest) but must be completed prior to C5 and prior to RT administration, if the latter is required. The post-C4 scan review visit can be combined with the C5D1 visit pre-infusion. The post-C8 scan review can be combined with the pre-RT visit if RT is required. Up to one week's delay between cycles for restaging is allowed. Participants who do not demonstrate progression on either restaging scan will undergo RT and/or surgery depending on treatment arm.

5.3.4 Radiation

Patients with borderline resectable pancreatic adenocarcinoma will receive radiation therapy 2-4 weeks after receiving last dose of chemotherapy as part of this trial. This section outlines the general guidelines for radiation planning and target volumes. These may be modified as part of each module.

5.3.4.1 Simulation

All patients must undergo CT simulation in the supine position with a customized immobilization device.

- Patients will be positioned supine in an Alpha Cradle or equivalent immobilization device that will be custom-made for each patient.
- Administration of IV and oral contrast is required for target and normal tissue delineation unless patient has a contrast allergy refractory to premedication or at the discretion of the treating physician. A pretreatment renal scan to assess kidney differential will be performed prior to initiation of treatment as clinically appropriate.
- MRI simulation may be performed in the treatment position and later fused to the CT simulation scan to assist in target volume delineation, or if IV contrast cannot be used, but this is not required.

5.3.4.2 Treatment planning

- Only ≥ 6 MV photons are permitted

- Particle therapy is not permitted.
- Target Volumes:
 - Gross Tumor Volume (GTV):
 - The GTV will be created in the same manner irrespective of form of radiation therapy delivered.
 - The GTV will include the primary pancreatic tumor and any grossly involved locoregional lymph nodes.
 - The diagnostic CT, respiratory-correlated 4D-CT scan, pancreas protocol CT, MRI, and/or the FDG-PET/CT scan (when available) should be reviewed to facilitate accurate delineation of the GTV.
 - Clinical Target Volume (CTV):
 - For pancreatic head, body, or tail tumors, the celiac and superior mesenteric arteries (SMA) should be contoured starting from the origin of the aorta.
 - A tumor-vessel interface (TVI) may be created for cases in which the tumor is in direct contact with a segment of portal vein, superior mesenteric vein, superior mesenteric artery, and/or celiac artery. This contour should include the entire circumference of the blood vessel(s) in contact with tumor as visualized on the CT and/or MRI.
 - Elective regional nodal irradiation (porta hepatis, celiac, pancreaticoduodenal, superior mesenteric artery) otherwise may be performed, but is generally not encouraged unless the treating physician thinks it is needed to cover gross tumor or grossly involved lymph nodes.
 - Generally, the CTV should be a combination of the celiac artery contour, the SMA contour, and the TVI contour (if applicable) and is expanded at least 1-2 cm around the combined structures of GTV, and regional nodes. Smaller margins are preferred for the CTV expansion if possible. After appropriate expansion to PTV, the area will receive the prescription dose for conventional radiation therapy.
 - Planning Target Volume (PTV):
 - For conventional radiation therapy, the PTV is expanded from the CTV using a 3-5 mm uniform expansion.
 - The physician should review the expansions to confirm the targets are covered throughout the respiratory cycle on the 4D CT scan.
 - Techniques of radiation delivery that are acceptable include 3D conformal, intensity modulated radiation therapy, and volumetric modulated arc therapy (or similar) using photon (or conventional x-ray) radiation.
 - Organs at Risk (OARs):
 - The spinal cord, bilateral kidneys, liver, stomach, duodenum, and other small bowel should be contoured carefully.
 - Radiation dose to OARs must be minimized.
 - Conventional radiation therapy constraints

- Greater than 95% of the PTV should receive the prescription dose.
- Quality assurance: All treatment plans should be reviewed by the radiation oncology collaborators ([name] and [name]) to confirm proper target coverage and dose constraints are met. This should happen within one week of beginning radiation therapy +/- 3 days.

Description	Planning System Name	Constraints
PTV	PTV	PTV covered by Rx dose > 95%
OAR		Constraints
Duodenum	Duodenum	Dmax < 40 Gy
Bowel	Bowel	Dmax < 35 Gy
Stomach	Stomach	Dmax < 40 Gy
Liver	Liver	Mean < 20 Gy
Combined Kidneys	Kidneys	Each with V10 < 33%
Spinal Cord	Spinal_Cord	Dmax < 35 Gy
Spleen	Spleen	Mean less than 6 Gy

5.3.4.3 Treatment

5.3.4.3.1 Treatment Interruptions

- Per Protocol: All treatments occur within the number of total fractions plus 2 calendar weeks.
- Variation Acceptable: All treatments occur within 16 to 21 calendar days of the original radiation schedule.
- Deviation Unacceptable: All treatments take 22 or more calendar days to complete, beyond the original radiation schedule.
- Questions regarding the radiotherapy section of this protocol, including treatment interruptions, should be directed to: [name] or [name].

5.3.5 Chemotherapy during radiation

All patients receiving radiation will receive concurrent chemotherapy with either Capecitabine or 5-FU as a continuous infusion (CI). The choice between capecitabine or 5-FU CI will be at the discretion of the treating physician and dose calculation per institutional standard. The recommended dose of capecitabine is 1650 mg/m² taken on the days of the radiation. It is recommended that 5-FU will be dosed Monday through Friday at 225mg/m² for the duration of the radiation. No specified timing of radiation treatment in relation to the chemotherapy is required.

5.3.6 Surgery

Surgical resection of the primary tumor and regional lymph nodes in the absence of disease progression 2-8 weeks following completion of neoadjuvant chemotherapy and/or radiation.

5.3.6.1 Surgical Quality Assurance

General considerations

Pancreaticoduodenectomy should occur within 2-8 weeks after the completion of neoadjuvant therapy. Staging laparoscopy may be performed at the time of planned laparotomy but is not required. Either standard or pylorus-preserving pancreaticoduodenectomy may be performed. Both laparoscopic and/or robotic pancreaticoduodenectomy are allowed. Surgical drains and enteral tubes (e.g. gastrostomy and/or jejunostomy tubes) may be placed at the discretion of the operating surgeon.

The operation should be performed in accordance with techniques espoused in the first edition of Operative Standards for Cancer Surgery, published by the American College of Surgeons and the Alliance for Clinical Trials in Oncology (68).

Specific considerations

Exploration of the peritoneal cavity should include evaluation for radiographically occult macroscopic peritoneal or hepatic metastases. Lymph node sampling or frozen section lymph node biopsy is not required or recommended as part of the intraoperative assessment for extra-pancreatic disease, and is at the discretion of the surgeon.

A standard lymphadenectomy should be performed routinely, to include lymph node stations 8a, 12a2, 12p2, 12b2, 12c, 13a, 13b, 14a, 14b, 17a, 17b. Other lymph node stations dissected should be detailed if performed in the operative report.

The retroperitoneal dissection along the medial edge of the uncinate process and the right lateral border of the superior mesenteric artery is believed to be an important oncologic part of the operation. All soft tissue to the right of the superior mesenteric artery (SMA) should be removed. This requires exposure and dissection along the right lateral border of the SMA.

Vascular resection and/or reconstruction of the superior mesenteric vein, portal vein, SMA/portal vein confluence, or hepatic artery will be performed at the discretion of the operating surgeon. In general, vascular resection should be performed when necessary to achieve an R0 resection. The operating surgeon or a vascular/transplant surgeon consult can perform this reconstruction. The technical details of the operation should be delineated in the operative report.

Intraoperative Frozen Section Assessment of Surgical Margins

Frozen section evaluation of the pancreatic parenchymal and hepatic (or bile) duct margins should be performed. In the event of a positive frozen section margin at either of these loci, further resection in an effort to achieve microscopically negative margins should be performed if possible. However, the extent of additional parenchymal resection should be left to the discretion of the operating surgeon.

The superior mesenteric arterial (SMA) margin should be evaluated on permanent section only.

Specimen Orientation for Surgical Pathology

The surgeon should ensure that the specimen is oriented for the surgical pathologist. Any segment of resected vascular structure (e.g. superior mesenteric or portal vein) should be identified and marked. Relevant margins evaluated by intraoperative frozen section (i.e. the hepatic (bile) duct, and pancreatic parenchymal) should be identified. The SMA margin (the soft tissue immediately adjacent to the SMA) should be separately inked using the principles outlined in the 7th edition AJCC staging system for exocrine pancreatic cancer. Note: The SMA margin cannot be identified accurately after the specimen has been fixed in formalin or after the specimen has been dissected for histopathologic analysis.

Aborting Surgery

The planned resection should be aborted if the operating surgeon identifies:

1. Metastatic disease in distant organs (e.g., liver). Presumed disease should be biopsied and confirmed as metastatic cancer on frozen section.
2. Localized cancer that is nonetheless, in the opinion of the operating surgeon, unsafe to resect. In such cases, the specific reasons for aborting the operation should be enumerated in the operative report.

In case of aborting surgery a tissue biopsy of the primary pancreatic tumor should be performed for correlative science as long as it is deemed safe by the primary surgeon.

Operative Note Dictation and Editing: Resection Classification

The attending surgeon should dictate the operative note. The operative report should contain:

1. A section detailing the operative findings with respect to the extent of disease and the primary tumor anatomy.
2. A statement as to whether or not the surgeon believes there is residual macroscopic tumor following completion of the resection.

The surgeon should integrate the operative findings with the microscopic surgical margins reported on the final pathology report in order to assign a resection classification prefix of R0, R1, or R2 (defined below). Whenever possible, this prefix should be added to the final operative note before finalizing the document or be documented in the first post-operative clinic visit note. An example of the final procedure description for a patient who underwent macroscopically complete tumor removal with a positive SMA margin on permanent section final pathology is: "R1 pylorus-preserving pancreaticoduodenectomy." The definitions for the resection classification that should be utilized in operative notes include:

- R0 – macroscopically complete tumor removal with negative microscopic surgical margins (bile duct, pancreatic parenchyma, and SMA margins)
- R1 – macroscopically complete tumor removal with any positive microscopic surgical margin (bile duct, pancreatic parenchyma, or SMA margins)

- R2 – macroscopically incomplete tumor removal with known or suspected residual gross disease

Surgical Pathology

A local pathologist experienced in the diagnosis of pancreatic adenocarcinoma should carry out pathological examination of the resected pancreatic tumor specimen.

Three primary margins (bile duct, pancreatic neck, and SMA) should be identified and inked by the surgeon and/or pathologist. Any segment of resected vascular structure (e.g. superior mesenteric or portal vein) should be identified and marked. The SMA margin (that tissue immediately adjacent to the SMA) should be separately inked according to the procedures and recommendations of the American Joint Commission on Cancer (AJCC) 7th edition staging system and the College of American Pathologists guidelines for reporting of resected exocrine pancreatic cancer (2012). The distance between the closest tumor cell and the inked SMA margin (the “SMA margin distance”) should be reported.

The tumor should be thoroughly sampled: At least 2 sections per cm should be submitted if there is grossly identifiable and histologically confirmed tumor. The entire tumor bed should be submitted if no viable tumor is identified in initial sections.

The AJCC 8th edition staging may be used for clinical reporting, but is not necessary for the trial purposes.

Frozen Section Assessment of Margins

Section assessment of bile duct and pancreatic neck margins should be performed by the local pathologist in all cases as requested by the surgeon.

Permanent Section Assessments and Final Pathology Report

The pathology report should contain all of the elements outlined in the College of American Pathologists guidelines for reporting of resected exocrine pancreatic cancer (2012). In particular, there should be specific comment on:

1. Histologic diagnosis with comment on the cell of origin (pancreatic vs. bile duct vs. ampulla)
2. Degree of differentiation (well, moderate, poor)
3. Total number of lymph nodes examined
4. Number of positive nodes
5. Final margins status for the bile duct, pancreatic parenchymal, and SMA margin
6. Distance (in mm) from the tumor to the inked SMA margin
7. Extent of tumor infiltration (if present) of the blood vessel wall for any resected major blood vessels including the maximum histologic depth of invasion (e.g., adventitia, media).

Treatment effect score will be determined using the following system:

- Treatment Effect Score I - 0% residual tumor cells in the specimen (pCR)
- Treatment Effect Score II - 1 to <5% residual tumor cells in the specimen
- Treatment Effect Score III - $\geq 5\%$ residual tumor cells in the specimen

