5.3.6.3 Surgical Quality Control

For all patients who undergo surgery during protocol treatment (including resection or not), the study chair and surgical co-chair will review the preoperative CT scan, the operative note, the surgical pathology report, and the adverse events associated with surgery (30 days postoperative) within 60 days of surgery. This requires that the study team complete the adverse event case report form (AE CRF) without delinquency.

Specific attention will be paid to deviations as listed above, as well as adverse events that occur in association with surgery. Operative reports and outcomes which, in the opinion of the study chair and surgical co-chair, raise potential patient safety concerns will be discussed and reviewed. Two operations which lead to such a discussion may lead to a surgeon being restricted from enrolling future patients.

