11 MEASUREMENT OF EFFECT

11.1 Antitumor Effect – Solid Tumors

For the purposes of this study, participants should be re-evaluated for response every 8 weeks.

In addition to a baseline scan, confirmatory scans should also be obtained 8 weeks following initial documentation of objective response.

Response will be evaluated during surgical resection and on histopathology. Major pathologic response will be defined as less than 5% viable tumor cells left in the pancreatic resection specimen.

Progression will be evaluated in this study using the new international criteria proposed by the Response Evaluation Criteria in Solid Tumors (RECIST) guideline (version 1.1) [*Eur J Ca* 45:228-247, 2009]. Changes in the largest diameter (unidimensional measurement) of the tumor lesions and the shortest diameter in the case of malignant lymph nodes are used in the RECIST criteria.

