11.1.7 Response Review

Not applicable

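### The trial is open label and MPR alone decides success, but the protocol does not withhold the treatment arm from the local pathologist who reads the specimen

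*Combined protocol and SAP*

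**What the plan says.** - **Open label.** Section 5.1: "Treatment with NIS793 will not be blinded".
- **Endpoint.** Section 11.1: "Major pathologic response will be defined as less than 5% viable tumor cells left in the pancreatic resection specimen". Section 13.1 gives the same cut-off of under 5%. It counts every patient who starts protocol therapy, including those never resected.
- **Success rule.** Section 13.1 claims success when the posterior probability that the Arm A MPR rate exceeds the control rate by more than 0.05 is above 0.74. No other outcome enters the rule.
- **Reader.** Section 5.3.6.1, Surgical Pathology: "A local pathologist experienced in the diagnosis of pancreatic adenocarcinoma should carry out pathological examination of the resected pancreatic tumor specimen".
- **Score.** The same section, under the final pathology report: "Treatment effect score will be determined using the following system". Three levels follow. Levels I and II (below 5% residual tumor cells) together make up MPR. The sentence names no scorer.
- **Who learns the arm.** Section 4.1 says that the registration and/or randomization confirmation "will be sent to the study coordinator(s) from the registering site, treating investigator and registering person". Section 4.4 adds, for other sites: "The registering party will email the participant study number and assigned arm or dose treatment level to the participating site". Neither section says who may be told afterwards.
- **Later review.** Section 5.3.6.3: "the study chair and surgical co-chair will review the preoperative CT scan, the operative note, the surgical pathology report". The Section 10 calendar has a Pathology Review row at surgery, which names no reader and no masking.

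**The concern.** The share of residual tumor cells is a visual estimate, and near 5% it calls for judgment. In an open-label trial, a reader who knows the arm may, without intending to, settle close calls differently in the two arms. An error confined to Arm A acts directly on the only quantity that decides the trial. Reading Arm A generously raises the chance of a false claim. Reading it strictly costs power. The 20% type I error limit and the 67.7% power in Section 13.1 hold only if the reading is unrelated to the arm, and the protocol takes no step to secure that.

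**Working it through.** **Step 1. Is the arm masked anywhere?** The places that come closest are these:

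| Place | What it does | Masks the arm? |
|---|---|---|
| 4.1 and 4.4 | Say who is sent the registration or arm information | No; onward disclosure is not restricted |
| 5.3.6.1 | Sets tissue sampling, report content and score levels | No |
| 5.3.6.3 | Study chair and surgical co-chair check surgical quality | No; no slide is re-read |
| 10, Pathology Review row | Schedules the review at surgery | No |
| 13.1 | Uses a numeric cut-off to limit subjectivity | No; it standardizes the cut-off only |
| Appendix B, 4.1 | Monitoring may include response assessments | No; it is optional and masking is not mentioned |

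The section headed "11.1.7 Response Review" is marked not applicable. It closes a section that is mostly about RECIST imaging, so little weight belongs on it. The Correlative Lab Manual is not among the documents and could not be checked.

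**Step 2. Reproduce the plan's own figures.** The inputs from Section 13.1 are n = 30 and 15, priors Beta(0.3, 0.7) and Beta(0.13, 0.87), margin 0.05 and threshold 0.74. For each of the 31 × 16 possible outcomes, compute Pr(p.e > p.c + 0.05 | data), declare success if it exceeds 0.74, and weight by the exact binomial probabilities.

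| True Arm A MPR (control 0.13) | Protocol Table 1 | Exact |
|---|---|---|
| 0.08 | 0.064 | 0.063 |
| 0.13 | 0.162 | 0.157 |
| 0.26 | 0.563 | 0.559 |
| 0.30 | 0.677 | 0.680 |
| 0.35 | 0.795 | 0.801 |
| 0.40 | 0.884 | 0.885 |

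All rows agree within 0.6 percentage points, and the 20% limit is met. The steps below use the exact values as the baseline: 15.7% false-claim probability and 68.0% power.

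**Step 3. Over-reading in Arm A only, true MPR 13% in both arms.** Let r be the share of patients resected and m the share of resected non-MPR specimens read as MPR. Unresected patients have no resection specimen to misread, so

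apparent Arm A rate = 0.13 + (r − 0.13) × m, with control unchanged at 0.13.

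Both r and m are assumptions, because the documents give neither for this trial. The 42% is the higher of two R0 rates that Section 2.1 reports from a cited randomized trial in borderline resectable disease. An R0 rate is only a lower bound on resection in that trial. The 60% and 80% are chosen to show a range.

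With m = 0.05:

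| r | Apparent Arm A rate | False-claim probability |
|---|---|---|
| 0.42 | 0.13 + 0.29 × 0.05 = 0.1445 | 19.3% |
| 0.60 | 0.13 + 0.47 × 0.05 = 0.1535 | 21.7% |
| 0.80 | 0.13 + 0.67 × 0.05 = 0.1635 | 24.5% |

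For other values of m:
- With m = 0.02, the result is 18.0% at 60% resected and 19.0% at 80%, both under the limit.
- The 20% limit is reached at an apparent rate of about 0.147. That needs m of about 5.9%, 3.7% or 2.6% at 42%, 60% or 80% resected.

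**Step 4. Under-reading in Arm A only.** If a share k of true Arm A MPRs is missed, the apparent rate is the true rate × (1 − k). At a true 30% versus 13% with k = 0.10, it is 0.30 × 0.90 = 0.27, and power falls from 68.0% to 59.1%. At 13% versus 13% with the same k, the false-claim probability falls to 12.9%.

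**The case against.** The strongest reply is that this is an omission, not a demonstrated exposure. No section tells the pathologist the arm. The trial is a declared open-label phase 2 of 45 patients with a 20% type I error limit. Section 13.1 chose a numeric cut-off to limit subjectivity, and Section 5.3.6.1 requires the whole tumor bed to be submitted when no viable tumor is seen at first. All of this is correct, and it keeps the point modest. It does not close the gap: a number still has to be estimated by someone, and fuller sampling does not hide the arm.

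The illustration can also be challenged, and that stands in part. It applies one misreading rate to all resected non-MPR specimens, although most disagreement would plausibly lie near 5%. Whether 5% over-reading crosses the 20% limit depends on the resected share; at 42% it does not.

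A reader might infer three stronger things that the documents do not support:
- **That nobody is assigned to score.** No sentence names the scorer. But the specimen examination goes to the local pathologist and the score sits under the final pathology report, so the assignment is implied.
- **That the result is biased or the type I error already fails.** No stated figure is wrong, and neither the presence nor the direction of bias is shown.
- **That the sensitivity of the rule to one specimen proves the point.** With 2/15 MPRs in control, 8/30 in Arm A succeeds (posterior 0.784) and 7/30 does not (0.700). This describes a small trial with a binary endpoint and would be the same under a perfectly masked reader.

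**Conclusion.** The point holds as a gap in protecting the primary endpoint. The trial is open label, MPR is the sole input to the success rule, and no section of the protocol keeps the arm from the local pathologist who examines the specimen and, by natural reading, scores it. It is not an error in the operating characteristics, which reproduce.

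The possible size is material but conditional. One-sided over-reading of 5% would put the false-claim probability between 19.3% and 24.5% for 42% to 80% resected. One-sided under-reading of 10% would cost about 9 points of power (68.0% − 59.1% = 8.9). These results rest on assumed misreading rates and resected shares, on error confined to Arm A, and on the Section 13.1 rates of 13% and 30%. If the Correlative Lab Manual already masks the reader, a cross-reference in the protocol would be enough. The change is recommended because it is cheap and has to be in place before specimens are scored.

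**What to change.** 1. Add to Section 5.3.6.1: *The local pathologist assigns and records the Treatment Effect Score without being told the treatment arm.*
2. Submit the specimen under the study number, described only as *neoadjuvant therapy per protocol*.
3. If the clinical report needs the arm, disclose it only after the score is recorded.
4. Record on the CRF whether the score was assigned before disclosure.

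The cost is one protocol sentence, one requisition instruction and one CRF item. No additional reader is needed and patient care does not change. The limits should be stated openly. Masking may fail through access to the chart. Section 2.5 expects NIS793 to alter fibroblasts and stroma, so the histology itself may hint at the arm. The CRF item is self-reported, so a failure of masking could go unnoticed. Random error around the 5% cut-off remains.
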